6.1.2 Investigational drugs

Table 6-1 Investigational and control drug

| Investigational (Name and Strength) | Pharmaceutical Dosage Form | Route of Administration | Supply Type | Sponsor (global or local) |
|-------------------------------------|----------------------------|-------------------------|--------------------------|---------------------------|
| ABL001 20 mg | Tablet | Oral use | Open Label; 30 ct bottle | Sponsor (Local) |
| ABL001 40 mg | Tablet | Oral use | Open Label; 30 ct bottle | Sponsor (Local) |

6.1.3 Additional study treatments

No other treatment beyond investigational drug and control drug are included in this trial.

6.1.4 Treatment Cohorts

This is an open label, three-cohort, multi-center phase IIIb study of asciminib (ABL001) monotherapy in previously treated patients with chronic myeloid leukemia on chronic phase (CML-CP) with and without T315I mutation

Patients without T315I mutation status are selected randomly between Cohort A (without T315I) and Cohort B (without T315I). Patients harboring the T315I mutation are allocated to Cohort C.

| Without T315I mutation | | With T315I mutation |
|------------------------|----------|---------------------|
| Cohort A | Cohort B | Cohort C |
| 40 mg BID | 80 mg QD | 200 mg BID |

6.1.5 Guidelines for continuation of treatment

Not Applicable see [Section 6.5.2](#)

6.1.6 Treatment duration

The patients are treated in the study up to end of study treatment period defined as up to 72 weeks after the last patient receives the first dose. Patients may be discontinued from treatment with the study drug at any time due to unacceptable toxicity, disease progression and/or at the discretion of the investigator or the patient.

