8.1.4 Visit Windows

Study visits from Week 1 Day 1 to Week 2 Day 1 should be completed on the designated date [with an allowed “visit window” of +/- 2 day for Week 1 Day 1 and Week 2 Day 1]. All visits up until Week 4 day 1 need to be performed live by the treating physician on the site.

Study visits from Week 4 to Week 72 (EOT) should be completed every 4 weeks on the designated date [with an allowed “visit window” of +/- 7 days]. After Week 4 day 1, remote visits can be performed using tele-medicine approach with the exception of visits on Weeks 12, 24, 36, 48 and 72.

A delayed visit will have no impact on the next planned visit. The next visit should be completed as scheduled in order to avoid accumulation of additional weeks.

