8.3.1.2 Clinical chemistry

Blood chemistry labs are to be analyzed at each scheduled visits by a central laboratory as specified in [Table 8-1](#) and [Table 8-6](#). Chemistry includes albumin, alkaline phosphatase, ALT (SGPT), AST (SGOT), total calcium, total calcium (corrected for albumin), creatinine, creatinine clearance, creatine kinase, potassium, magnesium, sodium, phosphate (inorganic phosphorus), direct bilirubin, indirect bilirubin, total bilirubin, total cholesterol, LDL cholesterol, HDL cholesterol, total protein, triglycerides, blood urea, Blood Urea Nitrogen (BUN), uric acid, amylase, lipase and fasting glucose.

HbA1c is analyzed at screening/baseline, week 12 and as clinically indicated.

The hepatitis markers HbsAg, HbcAb/anti-Hbc are analyzed at screening/baseline ([Table 8-6](#)).

Table 8-6 Clinical laboratory parameters collection plan

| Test Category | Test Name | Frequency |
|---------------|---|---|
| Hematology | Hemoglobin, platelets, red blood cells, white blood cells, WBC morphology with differential (basophils, eosinophils, lymphocytes, monocytes, neutrophils, promyelocytes, myelocytes, metamyelocytes, blast and other) | Screening/baseline, Week 1 Day 1, Week 2 Day 1, every 4 weeks from week 4 up to Week 72 (EOT) and as clinically indicated |
| Chemistry | Hemoglobin A1c | Screening/baseline, Week 12 and as clinically indicated |
| Chemistry | Creatinine clearance | Screening/baseline |

| Test Category | Test Name | Frequency |
|--------------------------------------|--|---|
| Chemistry | Albumin, alkaline phosphatase, ALT (SGPT), AST (SGOT), total calcium, total calcium (corrected for albumin), creatinine, creatine kinase, potassium, magnesium, sodium, phosphate (inorganic phosphorus), direct bilirubin, indirect bilirubin, total bilirubin, total cholesterol, LDL cholesterol, HDL cholesterol, total protein, triglycerides, blood urea or Blood Urea Nitrogen (BUN), uric acid, amylase, lipase, glucose (fasting) | Screening/baseline, Week 1 Day 1, Week 2 Day 1, every 4 weeks from week 4 up to week 72, (EOT), and as clinically indicated |
| Hepatitis markers | HbsAg, HbcAb /anti-Hbc | Screening/baseline |
| Serum Pregnancy test (if applicable) | Serum β -HCG testing | Screening/baseline, every 4 weeks up to week 72 (EOT), unscheduled |

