8.3.2 Cardiac Assessments

8.3.2.1 Electrocardiogram (ECG)

After the subject has rested approximately 10 minutes in a semi-supine position, standard 12-lead ECGs must be obtained in triplicate with a recommended minimal interval of 5 minutes between each ECG at the time points specified in Table 8-1, and Table 8-5. In this case recording of ECGs should be planned according to the true time of blood sample [REDACTED] rather than to the scheduled time point.

A standard 12 lead ECG will be performed:

- For Cohort A, B and C at screening and/or baseline, Week 1 day 1, Week 2 Day1, Week 4 Day 1, Week 12 Day 1, Week 24 Day 1, Week 36 Day 1, Week 48 Day 1, Week 60 Day 1, Week 72 Day 1 (end of study).
- Cohort C will require additional Week 8 Day 1 ECG in addition to the schedules mentioned above.

Table 8-2 ECG collection plan

| Week (or Cycle) | Time | ECG Type | Number of ECGs (per Visit) |
|---|---|----------|----------------------------|
| Screening/Baseline Day -21 to -1 / (all patients) | 3 serial ECGs at the screening visit | 12 Lead | 3 |
| Week 1 Day 1 | 3 serial ECGs at 2 h post dose | 12 Lead | 3 |
| Week 2 Day 1 | 3 serial ECGs pre-dose and at 2, 3, 4 h post dose | 12 Lead | 12 |

| Week (or Cycle) | Time | ECG Type | Number of ECGs (per Visit) |
|---|--------------------------------|----------|----------------------------|
| Week 4 Day 1 | 3 serial ECGs pre-dose | 12 Lead | 3 |
| Week 8 Day 1* | 3 serial ECGs pre-dose | 12 Lead | 3 |
| Week 12 Day 1 | 3 serial ECGs pre-dose | 12 Lead | 3 |
| Week 24 Day 1 | 3 serial ECGs pre-dose | 12 Lead | 3 |
| Week 36 Day 1 | 3 serial ECGs pre-dose | 12 Lead | 3 |
| Week 48 Day 1 | 3 serial ECGs pre-dose | 12 Lead | 3 |
| Week 60 Day 1 ⁺ | 3 serial ECGs pre-dose | 12 Lead | 3 |
| Week 72 Day (end of study) 1 | 3 serial ECGs 30 min post-dose | 12 Lead | 3 |
| Unscheduled or Unplanned sample | 3 serial ECGs | 12 Lead | 3 |
| 30 min +/- 5min allowed * Week 8 day 1 assessment is only applicable to Cohort C and in-person visit + only applicable to in-person visit | | | |

All ECGs performed will be independently reviewed. Instructions for the collection and transmission of these ECGs to the independent central reader will be provided in the [CABL001AUS04 ECG Manual].

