9.2 Study completion and post-study treatment

The patients are treated in the study up to end of study treatment period defined as up to 72 weeks after the last patient receives the first dose unless patients have discontinued treatment earlier. The end of the study will occur when the last patient enrolled (40 mg BID, 80 mg QD or 200 mg BID cohort) into the study completes 72 weeks of treatment or experience treatment failure.

The primary analysis (cut-off date) is defined as the date when all patients (in Cohort A, B and C) have been on study treatment for 24 weeks ([Section 12](#)) or discontinued earlier. Subsequent to this analysis, the primary clinical study report (CSR) will be developed. Following the cut-off date for the primary CSR, the study will remain open. Patients who are ongoing at the time of the primary analysis will continue to receive the study treatments (asciminib) during the study treatment period as defined above. The end of study treatment analysis will be conducted with a cut-off date 30 days after the end of study treatment period to ensure all available treatment data from all patients in the study is analyzed and summarized in a final CSR.

After the end of the study treatment period the assigned study treatment will be made available to patients who in the opinion of the Investigators are still deriving clinical benefit. This may be outside of this study through alternative options including, but not limited to, an expanded access/compassionate use /managed access program or access to commercial supplies in applicable countries.

10 Safety monitoring and reporting

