### On-treatment assessment/event and observation periods

For adverse event, reporting the overall observation period will be divided into two mutually exclusive segments:

- **Pre-treatment period:** from day of patient's informed consent to the day before first administration of study medication
- **On-treatment period:** from date of first administration of study medication to 30 days after date of last actual administration of any study medication (including start and stop date).

**Note:** Patients will be treated for up to LPFT + 72 weeks. This will be the last actual administration of study medication for each patient if the patient has not discontinued study medication earlier. After this period, the assigned study medication will be made available, may be outside of this study, to patients who in the opinion of the investigators are still deriving clinical benefit.

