**Table 2-1 Time windows for molecular response (BCR-ABL1 quantification by RQ-PCR)**

Assessment	Target day of assessment	Time Interval
Baseline	≤ 1	≤ Day 1#
Week 4	29	Day 2 to day 57
Week 12	85	Day 58 to day 127
Week 24	169	Day 128 to day 211
Week 36	253	Day 212 to day 295
Week 48	337	Day 296 to day 421
Week 72	505	Day 422 to day 589

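### Study treatment is defined to run to 72 weeks after the last patient's first dose, but every scheduled visit and test ends at each patient's own Week 72, and neither document says which governs

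*Protocol*

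**What the plan says.** **Treatment period, tied to the last patient.** Protocol 6.1.6 sets treatment at "up to 72 weeks after the last patient receives the first dose". Protocol 9.2 repeats it: the period is "defined as up to 72 weeks after the last patient receives the first dose unless patients have discontinued treatment earlier". Protocol 8.1.3 offers all patients drug until that end. SAP 2.1.1, under the on-treatment period, is firmer: "Patients will be treated for up to LPFT + 72 weeks. This will be the last actual administration of study medication for each patient", unless the patient stopped earlier. (LPFT is read here as the last patient's first dose.)

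**Assessment schedule, tied to each patient.** Protocol 8.1.4 states: "Study visits from Week 4 to Week 72 (EOT) should be completed every 4 weeks on the designated date". Table 8-6 schedules hematology "every 4 weeks from week 4 up to Week 72 (EOT) and as clinically indicated", and chemistry and pregnancy testing also stop at Week 72. The last scheduled ECG in section 8.3.2.1 is "Week 72 Day 1 (end of study"), and Table 8-2 agrees. Table 8-3 equates the Week 72 RQ-PCR sample with end of treatment. In Table 8-1 the only visible column after Week 72 is the 30-day safety follow-up.

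**Analysis windows.** In SAP Tables 2-1 and 2-2 the last molecular and hematologic response window is Week 72, "Day 422 to day 589".

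**The concern.** The two clocks agree only for the last patient enrolled. For everyone else there is an interval between own Week 72 and LPFT + 72 weeks in which one part of the plan says treatment may continue and another says treatment has ended. Sites could resolve this differently.

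The interval matters because several mandatory rules depend on routine tests in patients who may have no symptoms. Protocol Table 6-2 requires holds for Grade 3-4 cytopenia, for marked AST/ALT elevation and for asymptomatic Grade 3 amylase or lipase elevation. Protocol 9.1.1 requires discontinuation for BCR-ABL1 above 1% at 48 weeks or later, for loss of MR2, for confirmed loss of MMR and for a new T315I mutation. If dosing continues, these rules remain in force while the tests that trigger them are no longer scheduled.

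There is also a statistical effect. Duration of response is censored at the last adequate assessment (SAP 2.8.2). With no scheduled PCR after own Week 72, follow-up for that endpoint would in practice stop near Week 72 even in patients still on drug and still responding.

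**Working it through.** **1. Reproduce the SAP's target day.** Target day = 7 × week + 1. For Week 72: 7 × 72 + 1 = 505, as in SAP Tables 2-1 and 2-2. The other Table 2-1 target days after baseline (29, 85, 169, 253 and 337 for Weeks 4, 12, 24, 36 and 48) also reproduce. The schedule therefore counts from each patient's own Day 1. SAP Day 1 is the date of random allocation and the treatment clock starts at first dose; the two are taken here as the same day.

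**2. Where scheduled assessment ends.** Protocol 8.1.4 allows ±7 days, so the Week 72 visit closes on Day 505 + 7 = 512.

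**3. Where the last response window ends.** (589 − 1)/7 = 84, so it closes at Week 84. That is 589 − 505 = 84 days, or 12 weeks, after own Week 72.

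**4. The gap for one patient.** Let G be the time from that patient's first dose to the last patient's first dose. On the treatment-duration text, treatment can last 72 + G weeks.
- G above about 1 week: treatment time with no scheduled visit or test.
- G above 12 weeks: also treatment time after the last response window.

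**5. Is entry staggered?** The Protocol's amendment history reports no patient enrolled at 27-Jan-2021 and 25 at 22-Mar-2022. Against the planned 115, that leaves 115 − 25 = 90 to enter later if the target was met. Entry was therefore not simultaneous. The documents give neither the first nor the last patient's first-dose date, so the accrual length A cannot be derived.

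**6. Size over an assumed range of A.** Assumptions: 115 patients entering evenly over A weeks, no discontinuations. Longest treatment = 72 + A; mean G = A/2; most four-weekly visits missed by any patient = A/4, rounded down.

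| A (weeks, assumed) | Longest treatment (weeks) | Mean time past own Week 72 (weeks) | Most visits missed | Patients past Day 589 |
|---|---|---|---|---|
| 12 | 84 | 6 | 3 | 0 of 115 |
| 26 | 98 | 13 | 6 | 62 of 115 |
| 52 | 124 | 26 | 13 | 88 of 115 |
| 78 | 150 | 39 | 19 | 97 of 115 |
| 104 | 176 | 52 | 26 | 101 of 115 |

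These are upper bounds, because discontinuations reduce them. The visit counts apply to the earliest enrollee, not to a typical patient.

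**The case against.** The best reply is that the treatment text sets a ceiling (it says up to), while the operational text repeatedly labels own Week 72 as end of treatment or end of study. If each patient stops there, no dosing occurs without a schedule. A reader might infer that early enrollees will in fact be dosed without scheduled tests; the documents do not establish this. The reply does not remove the conflict, however. The SAP makes LPFT + 72 weeks the last administration for each patient still on drug, uses a final cut-off based on at least 72 weeks on treatment (SAP 2.1), and plans an exposure category of 72 weeks or more (SAP 2.4.1). Protocol 9.2 offers post-study access only after the common treatment period ends, so on the shorter reading the interval before that date is not covered.

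Three other stronger readings also fail.

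- *That data after Week 72 would be lost.* Table 8-1 marks AE/SAE recording and drug administration as continuous. Protocol 10.1.1 monitors adverse events for at least 30 days after the last dose. The SAP takes adverse events and laboratory values to 30 days after the last dose without visit windows, and censors overall survival at last contact drawn from many sources. Response rates, PFS, OS and secondary safety have no time point beyond 72 weeks.
- *That there would be no monitoring at all.* Clinically indicated laboratory tests and unscheduled ECGs and pregnancy tests remain available, and Protocol 8.3.3 ties pregnancy testing to the end-of-treatment visit. These do not replace a schedule for changes without symptoms.
- *That accrual was long.* The two enrolment counts do not show it; the first 25 patients could have entered quickly.

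Redacted rows of Table 8-1 cannot be checked.

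**Conclusion.** The inconsistency is real, runs through both documents and is resolved in neither. Followed as written, a patient enrolled before the last one either stops drug at own Week 72, against Protocol 6.1.6 and 9.2 and SAP 2.1.1, or continues with no scheduled laboratory, ECG, RQ-PCR or hematologic assessment.

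The consequences for safety and for duration of response hold only on the second branch. There, the thresholds of about 1 week (no scheduled visit) and 12 weeks (beyond the last response window) follow from the documents' own day counts, taking allocation and first dose as the same day. The number of patients and visits affected rests on an assumed accrual length and even entry, and is an upper bound. No sample-size figure changes. The point should be settled because it bears on patient safety and is cheap to correct.

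**What to change.** Reconcile the treatment-duration text (Protocol 6.1.6 and 9.2, SAP 2.1.1) with the assessment schedule (Protocol Table 8-1, section 8.1.4, and Tables 8-2, 8-3 and 8-6) so that, for each patient, the treatment period and the scheduled assessments end at the same point. Then align the SAP's on-treatment text with the result. If treatment beyond own Week 72 is retained, the SAP should also state how response assessments after Day 589 enter duration of response; new windows for response rates are not needed, since no rate is reported beyond 72 weeks. Which duration is right is for the sponsor to decide.

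The cost is wording in two documents. If the schedule is lengthened, there is also the site and laboratory work of the added visits.

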6.1.6.1 Treatment beyond disease progression

Not Applicable

6.2 Other treatment(s)

6.2.1 Concomitant therapy

The patient must be told to notify the investigational site about any new medications he/she takes after the start of the study drug. All medications (other than study drug and including over-the-counter treatment and nutritional or vitamin supplements) and significant non-drug therapies (including physical therapy, herbal/natural medications and blood transfusions) administered during the study must be listed on the “Concomitant Medications/Significant non-drug therapies” section of the eCRF.

Chronic medication should be maintained at the same dose and schedule throughout the study period, as medically feasible.

All prior antineoplastic surgery, chemotherapy, biologic, immunologic and radiation therapy must be recorded in the “Prior antineoplastic therapy” section of the eCRF.

In general, concomitant medications and therapies deemed necessary for the supportive care and safety of the patient are allowed, provided their use is documented in the patient records and on the appropriate case report form, including the medication’s duration (start and end dates or if continuing at final exam). These include blood and platelet transfusions for patients with anemia and with thrombocytopenia.

Permitted concomitant therapy

Drugs that affect gastric pH

Asciminib does not have a pH-dependent solubility. Drugs that elevate gastric pH will not affect asciminib absorption. All acid reducing agents are allowed.

6.2.1.1 Permitted concomitant therapy requiring caution and/or action

The *in vivo* potential of asciminib to interact with sensitive CYP3A4/5, CYP2C8 and CYP2C9 substrates has been evaluated and would indicate a minimal or negligible risk (Section 1.1.2.1). Therefore CYP3A4/5, CYP2C8 and CYP2C9 substrates with narrow therapeutic index (NTI) should be used with caution.

As CYP3A4/5 inhibitors may decrease the metabolism of asciminib and resulting in increased plasma concentrations and increased exposure, we recommend using them with caution at asciminib 40 mg BID and 80 mg QD. Note: at asciminib 200 mg BID the use of strong CYP3A4/5 inhibitors should be avoided (see 6.2.2).

In recombinant cellular expression systems, asciminib was identified as a substrate of BCRP ($K_m \approx 4 \mu\text{M}$) and P-gP (K_m could not be estimated due to insufficient saturation of efflux activity). Inhibitors of BCRP and P-gP may increase asciminib concentration. Based on human ADME study, P-gp may represent maximally 24% of the total clearance resulting in modest increase in AUC. Therefore, both BCRP and P-gp inhibitors should be administered with caution. If a medication listed in [Section 16](#) appears on both the list of prohibited and the list of medications to be used with caution, the medication is prohibited.

6.2.1.2 Use of bisphosphonates

The use of bisphosphonates regardless of indication is allowed.

6.2.2 Prohibited medication

Other anticancer agents

The administration of any other anticancer agents including chemotherapy and biologic agents is not permitted except for anti-cancer treatments of newly diagnosed solid cancers (e.g. prostate cancer) that would not impact the level of minimal residual disease of patients. These patients may remain in the current study after consultation with Novartis. The administration of other tyrosine kinase inhibitors indicated for treatment of CML are **not** allowed.

Strong CYP3A inducers

Any strong CYP3A inducers should be discontinued 7 days before the first dose of study medications.

Every effort should be made NOT to concomitantly administer strong CYP3A inducers during the study. If administration of a strong CYP3A inducer cannot be avoided during the study and cannot be switched to an alternative therapy, investigator should exercise caution while patient is on study treatment.

Cohort C only (200 mg BID): Strong CYP3A inhibitors

Any strong CYP3A inhibitors should be discontinued 7 days before the first dose of study medications.

Every effort should be made NOT to concomitantly administer strong CYP3A inhibitors. CYP3A inhibitors may decrease the metabolism of asciminib and resulting in increased plasma concentrations and increased exposure. If administration of a strong CYP3A inhibitor cannot be avoided during the study and cannot be switched to an alternative therapy that does not strongly inhibit CYP3A, asciminib must be interrupted.

A list of cytochrome P450 isoenzymes and CYP3A inhibitors may be found at medicine.iupui.edu/CLINPHARM/ddis/clinical-table.

A classification of CYP3A SmPC can be found in Section 16, [Table 16-2](#).

Further information can also be found in the following reference ([Venkatakrishnan et al 2001](#)).

UGT1A/2B inducers

The use of strong inducers of UGT1A/2B is prohibited during the study.

If administration of UGT1A/2B inducer cannot be avoided during the study and cannot be switched to an alternative therapy, temporary interruption of study treatment is NOT needed.

QT prolonging agents

As far as possible avoid co-administering drugs with a “Known”, “Possible” or “Conditional” risk of Torsades de Pointes (per www.crediblemeds.org/) during the course of the study:

- If concomitant administration of drugs with a “Known risk of Torsades de Pointes” is required and cannot be avoided, study drug must be interrupted. If, based on the investigator assessment and clinical need, study treatment is resumed, close ECG monitoring is advised.
- If during the course of the study, concomitant administration of a drug with “Possible risk” or “Conditional risk of Torsades de Pointes” is required, based on the investigator assessment and clinical need, study treatment may be continued under close ECG monitoring to ensure patient safety.

A list of drugs associated with QT prolongation and/or Torsades de Pointes is available online at www.crediblemeds.org/.

Herbal medications

Herbal preparations/medications are not allowed throughout the study. These herbal medications include, but are not limited to: St. John’s wort, Kava, ephedra (ma huang), ginkgo biloba, dehydroepiandrosterone (DHEA), yohimbe, saw palmetto, and ginseng. Patients should stop using these herbal medications 7 days prior to first dose of study drug.

